7.4.2 Discontinuations from Study Therapy

Discontinuation from study therapy is defined as subject's termination of the study medication without resumption prior to study completion. Section 3.5 of the protocol mentions the reasons for which a subject must discontinue treatment.

Discontinuation from study therapy during the Double-Blind Period is captured on the case report form (CRF) pages. For the analysis of discontinuations from study therapy refer to [Section 7.3.1](#).

7.4.3 Treatment Compliance

The CRF for this study will capture information on injections of abatacept or matching placebo during the Double-Blind Period and injections of abatacept during the open-label period.

The number of subjects with missed injections (excluding missed injections due to premature discontinuation from the study) during the Double-Blind Period or in the cumulative abatacept period will be summarized by number of missed injections based on the As-treated analysis population by treatment groups. A corresponding listing for all subjects who skip any injection will be provided.

[REDACTED]

[REDACTED]

- [REDACTED]
- [REDACTED]
- [REDACTED]
- [REDACTED]
- [REDACTED]
- [REDACTED]
- [REDACTED]

[REDACTED]

[REDACTED]

7.5 Efficacy

All efficacy analyses will be provided using the modified ITT analysis population. In addition, a sensitivity analysis will be provided for the primary and key secondary endpoints using the ITT population (see [Section 6.3](#) for more details).

A hierarchical testing procedure will be applied for the primary endpoint (change from baseline in ESSDAI at Day 169) and the 2 key secondary endpoints (change from baseline in ESSPRI at Day 169 and change from baseline in the stimulated whole salivary flow at Day 169 among the subjects with stimulated whole salivary flow of at least 0.1 mL/min at both screening and baseline) to ensure the preservation of the overall type I error of 5%. The first key secondary endpoint will only be tested (at a significance level of 5%) if the test for the primary endpoint is statistically significant at a significance level of 5%. If both the test for the primary endpoint and the first key secondary endpoint are statistically significant (both at a significance level of 5%), then the second key secondary endpoint will be tested (at a significance level of 5%).

P-values will be presented for each of these 3 endpoints. However, endpoints should not be interpreted for significance if they have a rank lower than that endpoint whose null hypothesis was the first that could not be rejected. That is, the significance of endpoints should not be interpreted if they have a rank lower than that endpoint whose test was the first to be non-statistically significant (p-value > 0.05).

The proportion of subjects with a decrease in ESSDAI of at least 5 from baseline to Day 169 and the proportion of subjects with a decrease in the ESSPRI of at least 1 to Day 169 are not included in the hierarchical testing procedure, however a nominal p-value will be presented for this endpoint at Day 169

No other p-values will be presented, except for a few sensitivity analyses of the primary and key secondary endpoints (see [Section 7.1.5](#) for more details).

7.5.1 Primary Efficacy Analysis

The EULAR Sjögren's Syndrome Disease Activity Index (ESSDAI) is a systemic disease activity index that was designed to measure disease activity in subjects with pSS (see Protocol Appendix 3). The ESSDAI parameters are assessed by the investigators and the results from each assessment are recorded in site source records as well as entered into the corresponding eCRF. The ESSDAI total score will be calculated as described in [Section 8.1.1](#).

Details of the primary efficacy analysis including the model specifications and back-up models are given in [Section 7.1.3](#) also provides the sensitivity analyses for the primary endpoint.

In addition, in case that more than 10% of subjects in any treatment group have a relevant protocol deviation, then the primary efficacy analysis will be repeated excluding efficacy data from subjects with relevant protocol deviations, as described in [APPENDIX 2](#). A p-value will be provided.

The adjusted mean change from baseline in ESSDAI will also be presented graphically by treatment arm for the Double-Blind Treatment Period (from baseline up to Day 169), as well as the double-blind and open-label periods combined (from baseline up to Day 365).

7.5.2 Secondary and Exploratory Efficacy Analyses

7.5.2.1 Continuous Endpoints

The continuous key secondary endpoints defined in this study are:

- The mean change from baseline in ESSPRI at Day 169
- The mean change from baseline in the stimulated whole salivary flow at Day 169 among subjects with stimulated whole salivary flow of at least 0.1mL/min at both screening and baseline

The other continuous secondary endpoints defined in this study are:

- The mean change from baseline at all measured time points up to Day 169 in the DAS28-CRP among those with a tender plus swollen joint count ≥ 3 at baseline, among those with a tender plus swollen joint count < 3 at baseline and in the full population.
- The mean change from baseline at all measured time points up to Day 169 in the individual components of DAS28-CRP among those with a tender plus swollen joint count ≥ 3 at baseline, among those with a tender plus swollen joint count < 3 at baseline and in the full population.

- The mean change from baseline at all measured time points up to Day 169 in the ESSDAI in the full population, among those with stimulated whole salivary flow of at least 0.1mL/min at both screening and baseline, and among those with stimulated whole salivary flow of less than 0.1mL/min at screening or baseline.
- The mean change from baseline at all measured time points up to Day 169 in the ESSPRI in the full population, among those with stimulated whole salivary flow of at least 0.1mL/min at both screening and baseline, and among those with stimulated whole salivary flow of less than 0.1mL/min at screening or baseline.
- The mean change from baseline in the individual components of the ESSDAI at all measured time points up to Day 169 in the full population, among those with stimulated whole salivary flow of at least 0.1mL/min at both screening and baseline, and among those with stimulated whole salivary flow of less than 0.1mL/min at screening or baseline.
- The mean change from baseline in the individual components of the ESSPRI at all measured time points up to Day 169 in the full population, among those with stimulated whole salivary flow of at least 0.1mL/min at both screening and baseline, and among those with stimulated whole salivary flow of less than 0.1mL/min at screening or baseline.
- The mean change from baseline in Schirmer's test at all measured time points up to Day 169.
- The mean change from baseline in ocular staining score at all measured time points up to Day 169.
- The mean change from baseline in tear break-up time at all measured time points up to Day 169.
- The mean change from baseline in unstimulated whole salivary flow at all measured time points up to Day 169 in the full population, among those with stimulated whole salivary flow of at least 0.1mL/min at both screening and baseline, and among those with stimulated whole salivary flow of less than 0.1mL/min at screening or baseline.
- The mean change from baseline in stimulated whole salivary flow at all measured time points up to Day 169 in the full population, among those with stimulated whole salivary flow of at least 0.1mL/min at both screening and baseline, and among those with stimulated whole salivary flow of less than 0.1mL/min at screening or baseline.
- The mean change from baseline in stimulated whole salivary flow at all measured time points up to Day 169 among
 - subjects with non-zero value at baseline for ESSDAI glandular domain and with stimulated whole salivary flow of at least 0.1mL/min at both screening and baseline
 - subjects with non-zero value at baseline for ESSDAI glandular and with stimulated whole salivary flow of less than 0.1mL/min at screening or baseline.
 - subjects with zero value at baseline for ESSDAI glandular domain and with stimulated whole salivary flow of at least 0.1mL/min at both screening and baseline
 - subjects with zero value at baseline for ESSDAI glandular and with stimulated whole salivary flow of less than 0.1mL/min at screening or baseline.

- The mean change from baseline in unstimulated whole salivary flow at all measured time points up to Day 169 among
 - subjects with non-zero value at baseline for ESSDAI glandular domain and with stimulated whole salivary flow of at least 0.1mL/min at both screening and baseline
 - subjects with non-zero value at baseline for ESSDAI glandular and with stimulated whole salivary flow of less than 0.1mL/min at screening or baseline.
 - subjects with zero value at baseline for ESSDAI glandular domain and with stimulated whole salivary flow of at least 0.1mL/min at both screening and baseline
 - subjects with zero value at baseline for ESSDAI glandular and with stimulated whole salivary flow of less than 0.1mL/min at screening or baseline.

[REDACTED]

[REDACTED]

All these endpoints will also be assessed up to Day 365.

The details of the calculation of the total score for ESSDAI, total score for ESSPRI, salivary flow rate, DAS28-CRP, Schirmer's test, tear break-up time, ocular surface staining are provided in [Sections 8.1.1, 8.1.2, 8.1.3, 8.1.4, 8.1.5, 8.1.6, 8.1.7](#), respectively.

The 3 analyses of eye dryness as measured by Schirmer's test (ST), tear break-up time (TBUT), ocular surface staining (OSS) will be

- for the "study eye" at baseline. The study eye at baseline is defined as follows: the eye with the highest total score for OSS at baseline, will be selected as the study eye. In case both eyes have the same total score for OSS at baseline, the eye with the lowest ST at baseline will be selected as the study eye. If both eyes also have an equal ST at baseline, then the eye with the lowest TBUT will be selected as the study eye. If both eyes also have an equal TBUT at baseline, then the right eye will be selected as the study eye. The same study eye will be used for ST, TBUT and OSS analyses.
- for the non-study eye at baseline. This is the eye that is not the study eye at baseline.
- based on the average of the measurement for the two eyes on the same visit.

Double-blind analysis for key secondary endpoints at Day 169

Details (model specifications, back-up models and sensitivity analyses) are provided in [Section 7.1](#).

[REDACTED]

[REDACTED]

[REDACTED]

[REDACTED]

[REDACTED]

[REDACTED]

[REDACTED]

[REDACTED]

[REDACTED]

Table 7.5.2.1-1: Schirmer's Test Score

Schirmer's test score/5 minutes (mm)
0 - ≤ 2
3 - ≤ 5
6 - ≤ 10
> 10

Analysis from Day 1 up to Day 365

The continuous primary, secondary and exploratory endpoints in the list given above will be analyzed using the longitudinal repeated measures model given in [Section 7.1](#). For the non-key secondary and exploratory endpoints, the stratification variable by day interactions will be removed from the model (the baseline variable and baseline-by -day interaction will be kept). All timepoints of the Double-Blind Treatment Period and the open-label period (at which endpoint is collected) will be included. The treatment variable in the model is the original randomized treatment. This analysis will include all efficacy measurements collected up to last dose +42. The baseline measurement in the model will correspond to the variable that is analyzed. The modified ITT population will be used. In addition, some of these endpoints (see [Section 4.2](#) and [4.3](#)) will also be analyzed for the following 2 subgroups:

- subgroup of subjects with stimulated whole salivary flow of at least 0.1mL/min at both screening and baseline
- subgroup of subjects with stimulated whole salivary flow of less than 0.1mL/min at screening or baseline.

The subgroup analyses mentioned in the 2 bullets above will only be provided if there are at least 10 subjects in each treatment group in each of the subgroups

The longitudinal repeated measures model for these subgroup analyses will not include the stimulated salivary flow stratification variable. At each timepoints the adjusted changes for the 2 treatments will be provided. No treatment differences will be provided for the open-label timepoints.

Plots of the adjusted mean changes (95%) over time (from Day 29 up to Day 365) per treatment group will be provided for the primary and key secondary endpoints.

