3.1.1 Screening Period

Eligibility will be based on specified inclusion and exclusion criteria, medical history, disease activity and safety assessments. The screening phase will last for a minimum of 7 days and a maximum of 28 days. Subjects who experience an acute infection or initiate treatment for latent TB may extend the screening period to 56 days. If the screening period extends beyond 28 days, a second screening visit will be required within 28 days prior to randomization.

Eligible subjects will have been diagnosed with Sjögren’s syndrome based on the proposed 2015 ACR/EULAR Classification Criteria ([Appendix 3](#)) and will have an ESSDAI score of at least five points at screening ([Appendix 6](#)). Subjects must be anti-SSA/Ro positive at screening and at least 124 subjects (72%) must have a stimulated salivary flow of at least 0.1 mL/min at screening and randomization.

Subjects taking hydroxychloroquine are permitted to continue this medication provided that the therapy has been taken for at least 12 weeks and that the dose is stable for at least 4 weeks prior to randomization and remains stable throughout the study. Decreases in dose or discontinuation is permitted for adverse events or intolerance.

Subjects receiving oral corticosteroids must be on a stable dose and at the equivalent of ≤ 10 mg prednisone daily for at least 4 weeks prior to randomization. Subjects may not have received an IM, IV or IA administration of a corticosteroid within 4 weeks prior to randomization.

Stable doses of pilocarpine, cevimeline, and cyclosporine eye preparations, as well as artificial tears and saliva are permitted, but must not be used for an appropriate period prior to salivary and ocular testing. See [Section 3.4.1.2](#) for specified times for each assessment.

Approximately 172 subjects in total will be randomized in a 1:1 ratio to 125 mg SC weekly of abatacept or placebo (86 subjects per arm). Randomization will be stratified globally by current use of corticosteroids, current use of hydroxychloroquine, and by stimulated salivary flow (< 0.1 mL/min, ≥ 0.1 mL/min).

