3.3.1 Inclusion Criteria

1. Signed Written Informed Consent

- a. Subject is willing to participate and has signed informed consent.

2. Target Population

- a. Subjects must meet the proposed 2015 ACR/EULAR Classification Criteria for SS (Sjögren’s Syndrome) ([Appendix 3](#)), as specified for pSS (primary Sjögren’s Syndrome).

- i. If a prior labial salivary or parotid gland biopsy was performed, information will be reported in the CRF and the report should be obtained for the source documents.
- b. Subjects should have pSS that is refractory to symptomatic or local therapy (eg, NSAIDs).
- c. ESSDAI \geq 5 at screening.
- d. Positive anti-SSA/Ro at screening.
- e. Stimulated salivary flow of at least 0.1 mL/min at screening and randomization in at least 124 subjects (72%). Enrollment of subjects with less than 0.1 mL/min of stimulated salivary flow at screening and/or randomization may be closed after 48 of such subjects are randomized.
- f. Subject Re-enrollment: This study permits the re-enrollment of a subject that has discontinued the study as a pre-treatment failure (ie, a “screen failure”, the subject has not been randomized / has not been treated). If re-enrolled, the subject must be re-consented and will receive a new PID.

3. Age and Reproductive Status

- a. Males and Females, ages \geq 18 (or age of majority).
- b. Women of childbearing potential (WOCBP) must have a negative serum or urine pregnancy test (minimum sensitivity 25 IU/L or equivalent units of HCG) within 24 hours prior to the start of study drug.
- c. Women must not be breastfeeding.
- d. Women of childbearing potential (WOCBP) must agree to follow instructions for method(s) of contraception for the duration of treatment with study drug(s) (abatacept/placebo) plus 5 half-lives of study drug (70 days) plus 30 days (duration of ovulatory cycle) for a total of 100 days post-treatment completion.
- e. Males who are sexually active with WOCBP must agree to follow instructions for method(s) of contraception for the duration of treatment with study drug(s) (abatacept/placebo) plus 5 half-lives of the study drug (70 days) plus 90 days (duration of sperm turnover) for a total of 160 days post-treatment completion. In addition, male subjects must be willing to refrain from sperm donation during this time.

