8.3.2 Secondary Endpoint(s)

Key Secondary Endpoints

- The mean change from baseline in ESSPRI at Day 169.
- The mean change from baseline in the stimulated whole salivary flow at Day 169 among subjects with stimulated whole salivary flow of at least 0.1 mL/min at both screening and baseline.

Other Secondary Endpoints

[figure not shown]
- The mean change from baseline at all measured time points up to Day 169 in the DAS28-CRP among those with a tender plus swollen joint count ≥ 3 at baseline, among those with a tender plus swollen joint count < 3 at baseline and in the full population.
- The mean change from baseline at all measured time points up to Day 169 in the individual components of DAS28-CRP among those with a tender plus swollen joint count ≥ 3 at baseline, among those with a tender plus swollen joint count < 3 at baseline and in the full population.
- Proportion of subjects who achieve a minimally clinically important change (of at least 3 points) in the ESSDAI at all measured time points up to Day 169 in the full population, among those with stimulated whole salivary flow of at least 0.1 mL/min at both screening and baseline, and among those with stimulated whole salivary flow of less than 0.1 mL/min at screening or baseline.
- Proportion of subjects who achieve a minimally clinically important change (of at least 5 points) in the ESSDAI at all measured time points up to Day 169 in the full population, among those with stimulated whole salivary flow of at least 0.1 mL/min at both screening and baseline, and among those with stimulated whole salivary flow of less than 0.1 mL/min at screening or baseline.
- Proportion of subjects who achieve a minimally clinically important change (of at least 1 point) in the ESSPRI at all measured time points up to Day 169 in the full population, among those with stimulated whole salivary flow of at least 0.1 mL/min at both screening and baseline, and among those with stimulated whole salivary flow of less than 0.1 mL/min at screening or baseline.
- The mean change from baseline at all measured time points up to Day 169 in the ESSDAI in the full population, among those with stimulated whole salivary flow of at least 0.1 mL/min at both screening and baseline, and among those with stimulated whole salivary flow of less than 0.1 mL/min at screening or baseline.

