7.5.2.2 Categorical Endpoints

The binary secondary endpoints defined in this study are:

- Proportion of subjects who achieve a minimally clinically important improvement (of at least 3 points) in the ESSDAI at all measured time points up to Day 169 in the full population, among those with stimulated whole salivary flow of at least 0.1mL/min at both screening and

Double-blind analysis over time

The binary endpoints given above at each timepoint (at which endpoint is collected) up to Day 169 will be analyzed as specified in Section 7.1.4. The modified ITT population will be used. Missing values will be imputed as non-responders. In addition, the secondary binary efficacy endpoints will also be analyzed for 2 subgroups:

- subgroup of subjects with stimulated whole salivary flow of at least 0.1mL/min at both screening and baseline
- subgroup of subjects with stimulated whole salivary flow of less than 0.1mL/min at screening or baseline.

The subgroup analyses mentioned in the 2 bullets above will only be provided if there are at least 10 subjects in each treatment group in each of the subgroups.

The logistic model for these subgroup analysis will not include the stimulated salivary flow stratification variable.

The response rate (%) and 95% CI over time will be plotted for each treatment group up to Day 169 for the secondary binary endpoints.

Analysis from Day 1 up to Day 365

The binary endpoints given above at each timepoint in double-blind and open-label period up to Day 365 will be summarized by a point estimate for the response rate and corresponding 95 % CI for the 2 original randomized treatment arms. No treatment differences will be provided for any timepoints during the open-label period.

The modified ITT population will be used. Missing values will be imputed as non-responders. In addition, the secondary binary efficacy endpoints will also be analyzed for 2 subgroups:

- subgroup of subjects with stimulated whole salivary flow of at least 0.1mL/min at both screening and baseline
- subgroup of subjects with stimulated whole salivary flow of less than 0.1mL/min at screening or baseline.

The subgroup analyses mentioned in the 2 bullets above will only be provided if there are at least 10 subjects in each treatment group in each of the subgroups.

The response rate (%) and 95% CI over time will be plotted for each treatment group during the double-blind and open-label periods up to Day 365 for the secondary binary endpoints.

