7.5.2.3 Subgroup Analyses

All analyses described in this section will be performed on the modified ITT Analysis Population. All subgroups will be defined based on the data as entered on the CRF; no IWRS will be used for any subgroup analysis.

Table 7.5.2.3-1 shows the subgroups of interest for analyses of the primary efficacy endpoint of Change from Baseline at Day 169 (ESSDAI). The analysis will be using the methods described in Section 7.1.3 for each level of each subgroup, except that all stratification variables and the baseline ESSDAI day-by-day interaction will be removed from the model for this subgroup analysis. If the value of the grouping variable cannot be determined for a subject, the subject will be excluded from the corresponding subgroup analysis. Only subgroups with at least 10 patients in both treatment arms will be considered.

A forest plot showing per subgroup the estimates per treatment group and the treatment differences will be provided. The sample size for each treatment group in the subgroup will be presented along with the adjusted mean change from baseline (with 95% CI) and the treatment difference (with 95% CI).

Table 7.5.2.3-1: Subgroups of Interest

Subgroup factor	Categories
Age	< 65 Years Old
	≥ 65 Years Old
Baseline Weight	< 60kg
	60 - 100kg
	> 100kg
Gender	Male
	Female
Race	White
	Black
	Asian
	Other
Geographic Region	North America
	South America
	Asia
	Europe
	ROW
	Baseline Hydroxychloroquine use as recorded in CRF
	No
Baseline oral corticosteroid use as recorded in CRF	Yes
	No
Baseline Stimulated Salivary Flow as recorded in CRF	< 0.1mL/min
	≥ 0.1mL/min

Table 7.5.2.3-1: Subgroups of Interest

Subgroup factor	Categories
Japan as recorded in CRF	Yes
	No
ESSDAI categories at Day 1	Low < 5
	Moderate $5 \leq \text{ESSDAI} \leq 13$
	High ≥ 14

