APPENDIX 1 DOCUMENT HISTORY

Table 9-1: Document History

Version	Statistician	Date	Notes/Revisions
1.0	[REDACTED]	13 September 2017	Original version
2.0	[REDACTED]	10 August 2018	
 • Subgroup analyses by stimulated salivary flow at screening and/or baseline < 0.1 (subgroup 1) and ≥ 0.1 (subgroup 2) will only be provided if there are at least 10 patients in each treatment group for both subgroups. • Subgroup analyses for mean change from baseline for ESSDAI at day 169 (by gender, race, region, ...) will only be provided if at least 10 subjects in each treatment group (instead of 10% currently in SAP v1.0). ESSDAI-by-time interaction removed from model. • Sensitivity analysis including the efficacy data after 42 days (post treatment up to day 169): only provided 
 - if at Day 169 there are at least 10% of subjects with missing data in either treatment group for the primary analysis - and on top, at Day 169 there are at least 10% more non-missing measurement in either treatment groups using all collected data (including post treatment) compared to number of non-missing measurement in primary analysis • Sensitivity analysis for MAR (tipping point and control-based pattern imputation): only if at Day 169 there are at least 10% of subjects with missing data in either treatment group for primary analysis • Forest plot: for treatment difference instead of by treatment group • Change wording ‘clinically important change’ to ‘clinically important improvement’. • Replacement of worst eye by study eye (and none study eye) • According to SAP v1.0 the minimal detectable change for 4 binary exploratory variables (stimulated and unstimulated salivary flow, Schirmer’s test, ocular staining score and tear break-up time) will be explored to define a meaningful change in each endpoint. Implementation in SAP v2.0: Proportion of subjects with 25% improvement and proportion of subjects with 50% improvement • Added: proportion of subject with ESSDAI < 5 up at Day 169

Table 9-1: Document History

Version	Statistician	Date	Notes/Revisions

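### The minimum-size rule for the two salivary-flow subgroups is joint, so a small low-flow group would also cancel the non-key secondary analyses in the well-filled subgroup with flow of at least 0.1 mL/min

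*SAP*

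**What the plan says.** SAP 7.5.2.1 (analysis from Day 1 up to Day 365) lists two subgroups: stimulated flow of at least 0.1 mL/min at both screening and baseline, and flow below that at either visit. It then says that the analyses in both bullets "will only be provided if there are at least 10 subjects in each treatment group in each of the subgroups". SAP 7.5.2.2 repeats the condition, "at least 10 subjects in each treatment group in each of the subgroups", twice for the binary endpoints, once for the double-blind analysis over time and once for the analysis up to Day 365. The version 2.0 entry in SAP Appendix 1 restates the rule: these analyses "will only be provided if there are at least 10 patients in each treatment group for both subgroups".

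For the forest-plot subgroups, SAP 7.5.2.3 uses the same threshold differently: "Only subgroups with at least 10 patients in both treatment arms will be considered".

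Protocol 8.3.2 defines a series of other secondary endpoints "among those with stimulated whole salivary flow of at least 0.1 mL/min at both screening and baseline", alongside the full population and the low-flow group, with no size condition. SAP 4.2 does the same in its visible part.

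On numbers, protocol 3.1.1 says "Approximately 172 subjects in total will be randomized in a 1:1 ratio". Protocol 3.3.1 (criterion 2e) requires at least 124 subjects with flow of 0.1 mL/min or more, and says that low-flow enrolment "may be closed after 48 of such subjects are randomized". It states no minimum for the low-flow group.

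**The concern.** The number of low-flow subjects has no bearing on whether a model can be fitted in the other subgroup, which is planned at about 62 per arm or more. As written, a shortfall in one group removes protocol-defined secondary results in the other. The subgroup that would go unreported is the one in which the second key secondary endpoint is tested. Readers would then lack the ESSPRI, responder and unstimulated-flow results in the same subjects, which put that test in context. If the sponsor restored them after seeing the counts, that would be a departure from the SAP which one phrase could have avoided.

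**Working it through.** **1. Is the condition joint?** The sentence governs both bullets and requires the count in each subgroup. Appendix 1 says both subgroups must qualify. SAP 7.5.2.3 shows how a subgroup-by-subgroup rule is worded in the same document. The joint reading is the natural one.

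**2. Planned sizes.** 172 − 124 = 48 low-flow subjects at the cap, about 24 per arm. 124/172 = 72%, about 62 per arm with flow of at least 0.1 mL/min. As a check on the plan's own figure for that subgroup: 0.165 / (0.275 × √(2/62)) = 3.34, and Φ(3.34 − 1.96) = 91.6%. The noncentral t gives 91.2%. The plan states 91%, so the figure reproduces.

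**3. When does the rule fail?** With m low-flow subjects, both arms can reach 10 only if m ≥ 20. At m ≤ 19 failure is certain, and the other subgroup then has at least 172 − 19 = 153 subjects (153/172 = 89%). For m ≥ 20 the answer depends on allocation. The documents give no block size or stratum shares, so the figures below rest on assumptions:
- Simple 1:1: P(fail) = 2 × P(Bin(m, 0.5) ≤ 9).
- Fixed 86/86 arms without stratification: hypergeometric.
- Permuted blocks of 4 within eight strata, with assumed shares of 30% on corticosteroids, 50% on hydroxychloroquine and 15% in Japan: simulation.

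| Low-flow m | Flow ≥ 0.1 mL/min (share of 172) | Simple 1:1 | 86/86 fixed | Blocks of 4 |
|---|---|---|---|---|
| 48 | 124 (72%) | about 0 | about 0 | – |
| 30 | 142 (83%) | 4% | 3% | about 0 |
| 24 | 148 (86%) | 31% | 27% | 3% |
| 22 | 150 (87%) | 52% | 49% | 20% |
| 20 | 152 (88%) | 82% | 81% | about 67% |
| ≤ 19 | ≥ 153 (≥ 89%) | certain | certain | certain |

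Blocks of 2 with the same shares give about 58%, 9% and under 1% at m = 20, 22 and 24.

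**4. Which endpoints are exposed?** Protocol 8.3.2 defines ten families by flow subgroup. Two drop out:
- Stimulated flow: the key-secondary model in SAP 7.1.3 is fitted in the ≥ 0.1 mL/min subgroup with no size condition. It has day and treatment-by-day terms and so covers Days 85 and 169, the only post-baseline flow visits up to Day 169.
- Mouth-dryness rating: SAP 7.7 handles it descriptively, with no visible size condition.

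That leaves 10 − 2 = 8: ESSDAI response of 3 points, ESSDAI response of 5 points, ESSPRI response of 1 point, ESSDAI change, ESSPRI change, ESSDAI components, ESSPRI components and unstimulated flow. ESSDAI change is exposed only in part, because the SAP 7.5.2.3 forest plot still shows Day 169 by flow. That plot uses baseline flow only and a reduced model.

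**5. After the change.** With a separate minimum, the ≥ 0.1 mL/min subgroup clears 10 per arm whenever its target of 124 is met. Only the low-flow results would drop out.

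**The case against.** The strongest case against is that little is lost. The rule is met at the planned 48, and nothing in the documents points to recruitment near 20. When failure is certain, the subgroup is at least 89% of the trial, so its results would sit close to the full-population results, which carry no size condition. The endpoints are outside the testing hierarchy, and SAP 7.5 gives p-values for only two of them, both nominal. Randomization is stratified, including by flow (protocol 3.1.1, SAP Table 7.3.2-1), which makes the simple 1:1 figures too high. All of this stands and limits the weight of the point. The qualification on stratification is that SAP 7.1 defines the subgroups from CRF data rather than the IWRS strata, so balance within them is not guaranteed.

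Redaction also matters. For continuous endpoints the visible rule is under the analysis up to Day 365, and text just before it is blacked out. That model does include every double-blind visit, and Appendix 1 states the rule without limiting it to a period. Only for binary endpoints, though, is the rule directly visible for the double-blind analysis.

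Paired reporting could be defended on the ground that the two subgroups are shown for contrast. The visible text gives no such rationale, and it would not explain why SAP 7.5.2.3 does otherwise.

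A reader might infer that results in 72% of the trial are at risk, or that all ten families are. The documents support neither. At 72% the rule is met, and two families are reported by routes without the condition.

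**Conclusion.** The rule is joint as written, and it can cancel well-populated, pre-specified secondary analyses for a reason unrelated to them. The defect is real but conditional and small. It touches at most eight non-key families up to Day 169, one of them partly. It bites only if low-flow recruitment falls far below the cap: certainly at 19 or fewer, and at 20 to 24 with a probability that depends on the unstated allocation scheme (82% to 31% under simple 1:1, lower with stratified blocks). No estimate, test, error rate or sample-size figure is wrong. A reader might also infer that the key secondary salivary-flow result could be lost. It could not, because SAP 7.1.3 specifies it without this condition. For continuous endpoints the conclusion carries the redaction caveat above.

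**What to change.** In SAP 7.5.2.1 (once) and 7.5.2.2 (twice), change the end of the sentence so that the count of 10 per arm refers only to the subgroup being reported. Each flow subgroup is then shown whenever it has at least 10 subjects in each arm. If the redacted text near 7.5.2.1 holds a matching sentence for the double-blind continuous analyses, change it in the same way.

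This needs no new data and does not affect the primary analysis, the hierarchy or the key secondary analyses. An undersized low-flow subgroup would still go unreported. The only downside is that one subgroup may appear without its counterpart, which a table footnote giving the low-flow count would explain. Minor priority.
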